We created an operational database of colonoscopy procedures and linked pathology notes housed in the VA CDW Text Integration Utility that can be semi-automatically updated with the most current data across the VA healthcare system. We have optimized a machine learning document classifier that uses the support vector machine algorithm to delineate a note as either a colonoscopy procedure note, or not. Our process allows to rapidly and prospectively confirm colonoscopy notes for NLP processing and colonoscopy quality reporting. Our NLP pipelines to extract colonoscopy procedure and pathology data have excellent performance (Table 1). The VA-EQuIP dashboard visually presents biannual and cumulative colonoscopy quality metrics to VA sites and providers, and provides comparison metric data at the local site and national level (Figure 2). All reports are created using Microsoft™ SQL Server Reporting Services 2013 and are hosted on a Microsoft SharePoint 2013 internal website. Access is controlled by both SharePoint memberships and local data access permissions.

Usability and [Pilot] Testing: In cooperation with our operations sponsor and partner, we obtained feedback and usability information on VA-EQuIP from the GI Field Advisory Committee. The committee members were provided access to their sites and individual data on colonoscopy quality. Respondents (N=5) provided feedback for internal consistency and were surveyed via the System Usability Scale (SUS).⁴⁹ The average SUS score for VA-EQuIP for 5 respondents was 87.0 (SD 9.9, range 77.5-100). A score >80.3 has been found to be in the top 10% of usability performance based on an ev

Table 1: NLP Performance for Colonoscopy Quality Metrics

Variable	PPV	Sensitivity	F Measure
ADR	98%	100%	99%
Screening Indication	89%	100%	94%
Cecal Intubation Rate	98%	99%	99%
Bowel Prep Adequate	100%	100%	100%

ates for NLP processing and colonoscopy quality reporting. and pathology data have excellent performance (**Table**

Facility Name:North Hospital **Provider Name:** Dr. C **Report Year:** 2017

[figure not shown]

Figure 2: VA-EQuIP Quality Dashboard

RESEARCH OVERLAP

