[Analysis Overview: Our goal is to compare the efficacy of VA-EQuIP versus usual care for the primary outcomes of overall (all indications) and screening indication ADR and secondary outcomes of bowel preparation quality and cecal intubation rate. We hypothesize that VA-EQuIP will lead to a higher rate of ADR, bowel preparation quality and cecal intubation relative to standard of care. We also hypothesize the effect will be particularly pronounced among providers who have low ADR, bowel preparation quality and cecal intubation rates prior to our intervention. The primary analysis takes advantage of the stepped wedge design by simultaneously comparing pre- and post- intervention data both within and across providers to evaluate the effect of the intervention while controlling for secular trends, which are uniform across sites. As a secondary analysis, we will implement a two-stage interrupted time-series and meta-regression analysis, which is commonly used to study intervention effects when an intervention occurs at different times within different providers. For all analyses, our primary inferences evaluate the ratio of ADR with versus without intervention for a given provider. However, our planned analyses also address the data structure, which nests patients within providers within sites.]

Eligibility / Inclusion criteria: We have identified 73 VA sites spanning VA (**Figure 4**) eligible for the study that have endoscopists with colonoscopy procedure and pathology notes in our database (SCS_Endoqual). In 2017, these 73 sites had 657 providers performing 155,926 colonoscopy procedures. The point of contact (i.e. GI section chief) at each site will be contacted by email about planned VA-EQuIP implementation and given specific instructions for accessing site data.

Exclusion criteria: VA facilities without existing colonoscopy procedure or pathology notes in our operational database will not be included in the study.

Consent: The national GI program office will implement VA-EQuIP as an operational initiative. We will obtain provider verbal consent by telephone, if deemed necessary by the IRB, for the evaluation.

Figure 4: VA-EQuIP sites

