Colonoscopy quality report card & reporting infrastructure: The VA-EQuIP quality reporting infrastructure includes 2 separate CDW databases with an extract, transform, loading (ETL) framework and secure SharePoint Site to visually present quarterly colonoscopy quality metrics (**Figure 2**). VA-EQuIP has been pilot tested and undergone iterative usability testing with the Gastroenterology Field Advisory Committee.

Data measures: CDW structured data include patient demographics and endoscopist name and specialty (e.g. gastroenterology, surgery). Variables derived from natural language processing of colonoscopy procedure and pathology notes include extent of exam, screening indication, and adenoma detection.

Outcome measures: The primary outcomes are overall and screening ADR for endoscopists after implementation of the quality report cards, [with an average follow up of 19.5 months (range 12-27 months).] Overall ADR is defined as the percentage of patients undergoing colonoscopy for any indication with one or more adenomas detected. Screening ADR is defined as the percentage of patients ≥ 50 years undergoing screening colonoscopy who have one or more adenomas detected. We will assess secondary outcomes measures, including cecal intubation rate and bowel preparation quality. Cecal intubation is defined as passage of the colonoscopy tip to a point proximal to the ileocecal valve so that the entire cecum is visible. The cecal intubation rate is the proportion of colonoscopies with cecal intubation documented in the procedure note. Bowel preparation quality is determined by the endoscopist for bowel cleanliness allowing polyp visualization and removal.

Primary Analysis -- Stepped Wedge at the Provider Level: We will utilize patient data aggregated to the provider level at monthly intervals to examine how the ADR changes pre- and post-intervention. A provider's monthly ADR is the ratio of the total number of the provider's positive ADR screening results to the total number of patients that the provider screened during the month. Prospective data collection will begin Jan 1st, 2020 and conclude Jun 30, 2022, a 30-month data collection period. Baseline data from 2019 will be included in our analysis to augment the pre-intervention time frame, to enable our intervention to start immediately. ADR

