For Aim 1, we have accounted for provider attrition and problematic data in our power calculation, based on our own and historical data provided by the national GI program office. The centralized infrastructure and NLP pipelines of VA-EQuIP will allow creation of reports for all providers in our database to ensure that the NLP system performance remains high throughout the project, several internal validation studies are planned. Each validation will involve a manual annotation of a random set of notes selected at each of the participating sites to create a reference standard. The system performance metrics will be calculated by comparing NLP system output and the reference standard. Since the NLP system was extensively evaluated during development, validation will be limited to measuring precision of extraction. If precision of extraction of each of the variable stays above 90%, the NLP system will be applied on the colonoscopy reports without changes. If evaluation detects decreased precision, detailed error analysis will be performed and system adaptation might be required. If system adaptation is performed, another round of validation will be required. In this case, both precision and recall will be evaluated. Colonoscopies performed on Veterans by providers outside of VA could be assessed for quality metrics using the NLP system contingent on the future integration of the colonoscopy and pathology data into VA CDW.

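### If more than about 90% of exams succeed, the 90% precision rule sets no floor on NLP specificity for cecal intubation and bowel preparation, so drift could go undetected

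*Combined protocol and SAP*

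**What the plan says.** The ongoing NLP checks are described under Sample Recruitment, in the Aim 1 paragraph on pitfalls and alternative plans. "Each validation will involve a manual annotation of a random set of notes selected at each of the participating sites", and NLP output is compared with that reference standard. Because the system was evaluated at length in development, "validation will be limited to measuring precision of extraction". The acceptance rule is: "If precision of extraction of each of the variable stays above 90%, the NLP system will be applied on the colonoscopy reports without changes". If precision drops, an error analysis follows and the system may be adapted. Only after an adaptation is a second measure added: "In this case, both precision and recall will be evaluated".

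The development results are in Table 1 (Data and Infrastructure), introduced with the statement "Our NLP pipelines to extract colonoscopy procedure and pathology data have excellent performance". The table gives PPV, sensitivity and F measure only. Cecal intubation has PPV 98%, sensitivity 99% and F 99%. Adequate bowel preparation has 100% on all three.

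The Aim 1 Analysis Overview names the "secondary outcomes of bowel preparation quality and cecal intubation rate" and hypothesizes that both improve. Under Outcome measures, "The cecal intubation rate is the proportion of colonoscopies with cecal intubation documented in the procedure note". Success is therefore the positive class for cecal intubation, and the Table 1 label shows the same for bowel preparation. The documents give no success rate for either outcome and no number of notes per validation.

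**The concern.** Precision asks how many of the exams called successes really were successes. When successes are very common, that share is high whatever the system does with the failures. The NLP error that would do most harm to these two outcomes is a failed exam (cecum not reached, preparation inadequate) read as a success. That is a loss of specificity, and neither the routine rule nor the extended check after an adaptation measures it.

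The stated purpose of the re-validation is to keep NLP performance high throughout the project, so drift is already the plan's own concern. Undetected drift of this kind would pull the observed rates toward 100% in control and intervention months alike and bias both secondary comparisons toward no effect. It would also hide from the dashboard the exams that it exists to flag.

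**Working it through.** **Inputs.** From the documents: the 90% precision bar; Table 1 PPV and sensitivity. Assumed, because not given: the true success rate π and the number of annotated notes. Se and Sp are sensitivity and specificity for success.

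**1. Table 1 reproduced.** F = 2 × PPV × Se / (PPV + Se). For cecal intubation, 2 × 0.98 × 0.99 / 1.97 = 0.985. With both inputs rounded to the nearest percent, the range is 0.980 to 0.990, so the stated 99% is consistent. True negatives do not enter F, so the table carries no direct information on failed exams.

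**2. What the bar demands of specificity.** Precision = Se·π / [Se·π + (1 − Sp)(1 − π)]. Setting this above 0.90 gives Sp > 1 − Se·π / [9(1 − π)]. At Se = 0.99:

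| True success rate π | Lowest Sp that meets the bar |
|---|---|
| 80% | 0.56 |
| 85% | 0.38 |
| 88% | 0.19 |
| 90% | 0.01 |
| 91% or more | none |

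The floor vanishes at π = 9 / (9 + 0.99) = 0.901. Above that, expected precision passes even at Sp = 0. An extractor that calls every exam a success has precision π and recall 100%, so adding recall after an adaptation would not expose it.

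**3. Finite samples.** With an assumed 100 notes, passing needs at least 91 correct. The all-success extractor passes with probability 0.2% at π = 80%, 5.5% at 85%, 22.6% at 88%, 72.2% at 92% and 97.2% at 95%.

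**4. Effect on the outcome.** Observed rate = Se·π + (1 − Sp)(1 − π). If Se and Sp are the same in the months compared, the observed difference is (Se + Sp − 1) times the true one. For an assumed true change from 92% to 95% (true ratio 0.95 / 0.92 = 1.033) and Se = 1:

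| Sp | Observed rates | Difference (points) | Ratio |
|---|---|---|---|
| 1.0 | 92.0% to 95.0% | 3.0 | 1.033 |
| 0.5 | 96.0% to 97.5% | 1.5 | 1.016 |
| 0.2 | 98.4% to 99.0% | 0.6 | 1.006 |
| 0 | 100% to 100% | 0 | 1.000 |

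**5. What Table 1 implies about specificity.** Sp = 1 − [Se·π(1 − PPV)/PPV] / (1 − π). For cecal intubation, Se = 0.99, PPV 98% with rounding limits 97.5% and 98.5%:

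| Assumed π | Sp at PPV 98% | Range from rounding of PPV |
|---|---|---|
| 90% | 0.82 | 0.77 to 0.86 |
| 95% | 0.62 | 0.52 to 0.71 |
| 97% | 0.35 | 0.18 to 0.51 |
| 98% | 0.01 | not possible (negative) to 0.26 |

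For example, at π = 95% and PPV 97.5%: 0.9405 × 0.025 / 0.975 = 0.0241, and 1 − 0.0241 / 0.05 = 0.52.

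For bowel preparation, take PPV as low as rounding allows (99.5%) and Se = 1. At π = 90%, 1 − (0.90 × 0.005 / 0.995) / 0.10 = 0.95. At π = 95%, 1 − (0.95 × 0.005 / 0.995) / 0.05 = 0.90. Specificity at those rates was therefore high in development.

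**The case against.** A reader might infer that the rule cannot fail whenever most exams succeed. The documents do not support that. A simple majority is not enough: at success rates of 80% or 88% the all-success extractor has expected precision below the bar. Even above 90% a sample can fail by chance, with probability 1 − 0.722 = 27.8% at a 92% rate with 100 notes. No success rate is stated for either outcome.

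A reader might also infer that the present system is already reading failures as successes. Nothing shows this. The 100% figures for bowel preparation argue against it, unless nearly all the development notes were adequate. The cecal figures do not establish it either: implied specificity depends on the unstated mix of development notes and moves widely with rounding, so no single attenuation figure can be taken from Table 1.

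Three further points have some weight. Drift could equally take the form of missed successes, for instance if note templates change. An extractor that gave every provider 100% would probably be noticed on the dashboard, although that is no formal check and partial loss of specificity would be harder to see. And the rule covers every variable, while screening indication has a development PPV of 89%. Read jointly, the rule would not be met at development values and an error analysis would follow. None of these steps, as described, measures failure-class accuracy for the two secondary outcomes, so the gap stands.

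Text beyond the start of the Project Management Plan was not available, so further validation detail there cannot be excluded.

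**Conclusion.** The point holds as a conditional gap in the safeguard. If true success exceeds about 90%, the precision bar places no lower limit on specificity in expectation, and recall after an adaptation does not supply one. Failed exams drifting into the success class could pass unnoticed and shrink the absolute effect by Se + Sp − 1. At the cecal values in Table 1 and an assumed 95% rate, that factor would lie between 0.99 + 0.52 − 1 = 0.51 and 0.99 + 0.71 − 1 = 0.70. This range shows how little the table settles; it does not estimate the trial's bias.

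The conclusion rests on an assumed success rate above about 90% and on equal error rates in the months compared. It concerns the two secondary outcomes only. The argument does not carry over to adenoma detection, where the plan works with a pre-intervention rate of 27.5% and positives are the minority.

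**What to change.** For cecal intubation and bowel preparation, keep the precision rule and add two measures from the randomly selected annotated notes, pooled across sites: specificity (the share of truly failed exams that the NLP reads as failed) and the precision of NLP-negative calls. Give confidence intervals, and prespecify a minimum for both before the NLP is applied unchanged. If annotators find failures and the NLP makes no negative calls, count that as not meeting the rule. Add the same two figures to Table 1 from the development data.

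Do not rely on sampling only NLP-negative notes, because failures misread as successes lie among the NLP-positive ones. If NLP-negative notes are oversampled to gain efficiency, weight for that selection when estimating specificity.

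The text change is small, and the two-by-two table should be available if annotation covers the random notes whatever the NLP called them. The real cost is precision, since failures may be few. At an assumed 95% success rate, 100 notes contain about 5 failures. At a specificity of 0.90 the approximate 95% half-width is then 1.96 × √(0.09 / 5) = 0.26. With an assumed 10 notes at each of 73 sites, 730 × 0.05 = 36.5 failures give 1.96 × √(0.09 / 36.5) = 0.10. Pooling is therefore needed, and some extra annotation may be too.
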